9 STATISTICS

9.1 Sample Size

A sample size of approximately 136 subjects (68 per treatment group) that are evaluable for efficacy (i.e. who have a Day 8 mLcVA measurement) is needed for the study.

All subjects will be randomized into the study in a 1:1 ratio to 1 of the 2 treatment arms (Nyxol or placebo), [REDACTED]

It is assumed that there will be approximately 15% drop-out. To account for this drop-out, a total of approximately 160 subjects will be randomized into the study.

9.2 Analysis Populations

Modified Intention-to-Treat: The mITT will include all randomized subjects who received at least 1 dose of study medication. The mITT will be used for the primary endpoint analysis and to analyze efficacy endpoints.

Per Protocol Population: The PP population includes all subjects in the mITT who received at least 5 doses of study medication during the first 7 days of dosing including the day prior to Day 8, have a Baseline and a Day 8 mLcVA measurement, and have no major protocol deviations. The PP population will be used to analyze efficacy endpoints.

All Randomized Population (ARP): The ARP will include all randomized subjects. This population is also known as the intention-to-treat (ITT) population. The ARP will be used in confirmatory efficacy analyses.

Safety Population (SP): The SP will include all randomized subjects who have received at least 1 dose of study medication. The SP will be used to summarize safety variables.

9.3 Statistical Methods

9.3.1 General Considerations

All continuous variables will be summarized by treatment and timepoint (as applicable) using descriptive statistics (n, mean, median, standard deviation, minimum, and maximum). All categorical variables will be summarized by treatment and timepoint (as applicable) using frequency counts and percentages.

All study data will be listed by treatment, subject and timepoint (as applicable).

All statistical tests will be performed using a significance level of 5% (two-tailed). The p-values for the analysis of secondary efficacy endpoints will be considered descriptive.

9.3.2 *Demographic and Baseline Characteristics*

Demographic and baseline characteristics such as age, race, and sex will be summarized by treatment group using the mITT, PP population, ARP, and the SP. These data will also be provided in by-subject listings.

9.3.3 *Subject Disposition*

Subject disposition, including randomization, and completion and withdrawal from the study will be summarized using the ARP. These data will also be provided in by-subject listings.

9.3.4 *Medical History and Prior/Concomitant Medications*

Medical history will be coded using the latest version of Medical Dictionary for Regulatory Activities (MedDRA) and will be summarized by treatment group using the SP.

Prior medications (medications with an end date prior to the date of randomization) and concomitant medications (medications with a start or end date after the date of randomization) will be coded using World Health Organization Drug Dictionary and will both be summarized by treatment group using the SP.

Medical history and prior and concomitant medications will also be provided in by-subject listings.

9.3.5 *Analysis of Efficacy*

Efficacy will be assessed using the mITT and PP population with subjects included in the treatment arm in which they were randomized. For the analysis of the primary efficacy endpoint, appropriate imputation techniques will be performed for missing observations if applicable; details will be provided in the study Statistical Analysis Plan. If the analysis using the PP population shows a positive effect for Nyxol at the 0.05 level of significance, the primary endpoint will be considered met. Confirmatory analyses may be performed using the ARP, with imputation performed for missing data. For the analysis of the secondary efficacy endpoints, only observed case data will be used. If warranted, confirmatory analyses using the ARP with imputation for missing data will also be performed for the secondary efficacy endpoints.

For all efficacy endpoints, Baseline values are defined as the screening assessment values on Visit 1 (Day 1).

Secondary efficacy endpoints are indicated in [Section 4.1](#).

Each of the continuous secondary efficacy endpoints will be analyzed using analysis of covariance (ANCOVA) with change from baseline as the dependent variable, treatment, [REDACTED], and the respective baseline value included as the covariate. Each ANCOVA will be performed using the mITT and PP population, with subjects included in their randomized treatment regardless of the treatment they actually received. The output from each ANCOVA will include the least squares mean (LSM) and standard error for both treatment groups, along with the placebo-corrected LSM, its 95% CI and associated p-value.

For each of the secondary endpoints related to percent of subjects achieving certain criteria, the analysis will be performed using a logistic regression model with treatment, light/dark irides, and the respective baseline as a covariate. For each analysis, the percentage of subjects in each treatment group meeting the criteria, the OR with 95% CI and p-value will be provided. For these endpoints, the mITT and PP population will be used with subjects included in their randomized treatment regardless of the treatment they actually received.

In addition, each secondary efficacy endpoint will be analyzed [REDACTED] using the same model and sensitivity analysis indicated above, as appropriate. Other subgroups, such as age, sex, and race, may be analyzed as well.

9.3.6 *Analysis of Safety*

Safety will be assessed using the SP with subjects included in the treatment group they actually received, regardless of their randomized treatment. Observed case data will be used; no imputation will be performed for missing safety data. A statistical analysis of conjunctival hyperemia will be conducted as described below; otherwise, no statistical analysis of safety data will be performed.

For HR and BP, baseline value is defined as the screening value. HR and BP values and change from baseline in the values will be summarized by treatment group and timepoint (Day 1, Day 8, and Day 15).

Observed values and change from baseline (Day 1) in conjunctival hyperemia at each visit (Day 8 and Day 15), will be summarized for the study eye, the non-study eye, and the best of either eye. Treatments will be compared using the same ANCOVA model proposed for the continuous secondary efficacy endpoints.

For IOP, baseline is defined as the baseline value of Visit 1 (Day 1). Observed values and change from baseline in IOP at Day 8 and Day 15 will be summarized for the study eye, the non-study eye, and the best of either eye.

Subject questionnaire values will be summarized by treatment group and timepoint (Day 1, Day 8, and Day 15).

Verbatim descriptions of AEs will be coded using MedDRA. Only TEAEs (those that occur after the first dose of study medication *or increasing in severity after initiation of study medication*) will be summarized. TEAEs and SAEs will be summarized by treatment group, by system organ class (SOC), severity, and relationship to study medication. Deaths, withdrawal from study medication due to AEs, and withdrawal from the study due to AEs will each be summarized by treatment group. Note that in MedDRA, ocular events are coded to the SOC of “special senses”. Thus, using SOC in the summaries will provide a separation of ocular and non-ocular AEs.

All safety data will be provided in by-subject listings.

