7.1.1. Modified Intention-to-Treat (mITT)

The mITT will include all randomized subjects who received at least 1 dose of study medication and have a Baseline and any Day 8 efficacy measurement. The mITT will be used for the primary endpoint analysis and to analyze efficacy endpoints, with subjects included in their randomized treatment regardless of the treatment they actually received.

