9. EFFICACY ANALYSES

Unless otherwise noted, efficacy will be assessed using the mITT and PP populations, with subjects included in their randomized treatment regardless of the treatment they actually received. For the analysis of the primary efficacy endpoint, imputation will be performed for missing data as described in [Section 7.3.2.3](#). If the analysis using the mITT Population shows a positive effect for Nyxol at the 0.05 level of significance, the primary endpoint will be considered met.

Confirmatory analysis of the primary efficacy endpoint will be performed using the ARP, also using imputation for missing data. For the analysis of the secondary efficacy endpoints, only observed case data will be used.

To formally test the significance of endpoints of interest beyond primary efficacy, endpoints will be tested in a predefined sequence using observed data only, each at the significance level 0.05, until the first nonsignificant test. The primary efficacy endpoint will be first in this sequence. The endpoints in the sequence are for the mITT population and study eye, and either Day 8 or Day 15. The sequence is specified in [Section 12.3](#).

All efficacy assessment data, regardless of whether they are included in the analysis, will be presented in by-subject listings.

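### Protocol 9.3.5 judges primary success on the PP set, while protocol 9.2 and the SAP use the mITT; both sets are also defined differently in the two documents, and the visible text of SAP 3.3 mentions none of this

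*Protocol*

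**What the plan says.** **Success rule.** Protocol 9.3.5 considers the primary endpoint met on this condition: "If the analysis using the PP population shows a positive effect for Nyxol at the 0.05 level of significance". SAP 9 has the same rule for the other set: "If the analysis using the mITT Population shows a positive effect for Nyxol at the 0.05 level of significance". SAP 9 also places its sequential testing there: "The endpoints in the sequence are for the mITT population and study eye, and either Day 8 or Day 15".

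**Primary analysis set.** Protocol 9.2 says: "The mITT will be used for the primary endpoint analysis and to analyze efficacy endpoints". SAP 7.1.1 agrees.

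**mITT definition.** Protocol 9.2: "The mITT will include all randomized subjects who received at least 1 dose of study medication". SAP 7.1.1 requires more: "at least 1 dose of study medication and have a Baseline and any Day 8 efficacy measurement".

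**PP definition.** Under protocol 9.2, PP subjects must "have no major protocol deviations. The PP population will be used to analyze efficacy endpoints". SAP 7.1.2 excludes a subject only for a major deviation judged to affect treatment outcome significantly. The dose-count condition and the Baseline and Day 8 mLCVA condition are the same in both documents.

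**Missing data.** Protocol 9.3.5 plans imputation for the primary endpoint where applicable, while protocol 9.4 puts the focus of the efficacy analysis on observed cases. SAP 7.3.2 imputes in the mITT analysis of the primary endpoint. SAP 9 adds: "Confirmatory analysis of the primary efficacy endpoint will be performed using the ARP, also using imputation for missing data".

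**Declared changes.** The visible text of SAP 3.3 lists the hierarchical analysis, the handling of the questionnaire as efficacy only, and two added secondary endpoints. It then says the SAP is otherwise consistent with the protocol.

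**The concern.** The rule that decides whether a registration study has met its primary endpoint should read the same wherever it is stated. Here the protocol contradicts itself (9.2 against 9.3.5) and contradicts the SAP, and the section meant to record such changes asserts consistency.

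Taken literally, the protocol's rule would rest a superiority claim on a set selected after randomization by doses taken, Day 8 attendance and deviations. The blinded review in SAP 8.2 limits the discretion over deviations. It does nothing about selection by dosing or attendance.

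The SAP's rule avoids that, but its mITT carries a post-randomization condition of its own under a name that the protocol defines without one. A reader of the study report who looks up mITT in the protocol would find a different set from the one analysed.

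**Working it through.** **1. The texts side by side.**

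| Item | Protocol | SAP |
|---|---|---|
| Set for the primary analysis | mITT (9.2) | mITT (7.1.1, 9) |
| Set that decides success at 0.05 | PP (9.3.5) | mITT (9) |
| mITT membership | randomized, at least one dose (9.2) | the same, plus Baseline and any Day 8 efficacy measurement (7.1.1) |
| PP exclusion for deviations | any major deviation (9.2) | only major deviations judged to have significant impact (7.1.2) |
| ARP analysis of the primary endpoint, with imputation | optional (9.3.5) | planned (7.3.2, 9) |

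One sentence, in protocol 9.3.5, stands against protocol 9.2, SAP 7.1.1 and SAP 9. That pattern suggests a slip.

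**2. What imputation can reach under each set.** Sort dosed subjects by their Day 8 data:

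- A: Day 8 mLCVA present.
- B: Day 8 mLCVA missing, another Day 8 efficacy measure present.
- C: no Day 8 efficacy data at all.

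| Set | Subjects it can contain | Subjects whose primary outcome could be imputed |
|---|---|---|
| PP (either document) | A, subject to the dose and deviation conditions | none |
| mITT, SAP | A, B | B |
| mITT, protocol | A, B, C | B and C, if imputation is applied |
| ARP | A, B, C and any never dosed | all those without Day 8 mLCVA |

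PP membership requires a Day 8 mLCVA value. Under the protocol's success sentence, the imputation planned in the same paragraph could therefore never affect the decision. Under the SAP's mITT, imputation reaches only group B. Group C is left to the ARP analysis, which does not define success.

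**3. Size of the mITT gap.** Inputs from protocol 9.1 and SAP 6: 136 evaluable subjects (68 per group), about 15% drop-out, about 160 randomized. The plan's own figure reproduces: 136 / (1 − 0.15) = 160. Evaluable means having a Day 8 mLCVA measurement (protocol 9.1), so the planned number without one is 160 − 136 = 24, or 24 / 2 = 12 per arm if balanced. Those 24 cover group B, group C and anyone never dosed, so on the planning assumption group C is 24 or fewer.

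Three provisions point to a smaller number. SAP 6 counts drop-out through to Day 15, so some of the 24 may have Day 8 data. Protocol 4.9.4 asks sites to make every effort to obtain Day 8 measurements before a subject leaves. SAP 7.3.3 assigns early-termination data to the closest visit.

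**4. Could redaction hide the disclosure in SAP 3.3?** The gap there follows a colon that introduces the two added secondary endpoints, so the missing text evidently names them. The closing sentence on consistency is visible.

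**The case against.** The strongest reply is that the operative rule is not really in doubt. Protocol 9.2 and the SAP agree on the mITT, and SAP 3.1 describes the SAP as a priori and final before unmasking. This largely stands: the mITT rule is the one likely to be applied. But no visible text says that the SAP overrides the protocol's criterion. Protocol 9.3.5 leaves only the imputation details to the SAP, protocol 13.5 allows protocol changes only by amendment, and SAP 3.3 claims consistency instead of a change. Reporting deviations in the study report (protocol 9.5) would come too late to fix the criterion.

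A reader might infer more than the documents support:

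- *That two rules give two chances of success and inflate the type I error.* No document lets success be claimed on either set. An either-set error rate would describe a rule that nobody proposes.
- *That the two PP sets will differ.* The clauses differ; the sets need not. They diverge only if some major deviation is judged to lack significant impact.
- *That the SAP removes subjects whom the protocol would certainly have analysed.* Protocol 9.4 focuses on observed cases, and 9.3.5 imputes only where applicable. If the protocol's mITT analysis is not imputed, group C adds nothing to it, and the gap shrinks accordingly.
- *That 24 is a maximum.* The 15% is a planning assumption.
- *That Phase 2 responder rates can turn the gap into a bias.* The severe night vision trial in protocol 2.2 was single-dose with measurements a few hours later, so it supplies no Day 8 rate.

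The SAP cites protocol amendment 3, and the visible protocol text carries no version number, so a version mismatch cannot be excluded. The conflict between protocol 9.2 and 9.3.5 lies within one document and does not depend on that.

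**Conclusion.** The point holds as a conflict in the stated success criterion and in two set definitions, left undeclared in the visible text of SAP 3.3. It should be fixed before unmasking.

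Its likely numerical effect is modest. If the SAP rule is followed, the primary test stays at 0.05. The mITT definition gap concerns roughly 24 of 160 subjects or fewer, on the planned 15% drop-out. It is smaller still if the protocol's mITT analysis would have used observed cases only. No bias in percentage points can be given, because the documents show no Day 8 responder rates and most of the imputation method is redacted. The ARP analysis with imputation is a partial safeguard, since it includes the subjects whom the SAP's mITT drops.

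**What to change.** **Before unmasking, in SAP 3.3:** state that primary success is judged on the mITT, that the PP analysis is supportive, and which mITT and PP definitions apply in place of protocol 9.2 and 9.3.5. Remove or qualify the consistency sentence accordingly.

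**Choice of mITT.** Either definition can work if it is stated once. The randomized-and-dosed set is preferable, because the planned imputation then covers dosed subjects with no Day 8 data. Adopting it means deleting the Day 8 condition from SAP 7.1.1. The SAP already plans to impute for the ARP, so no new method is needed.

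**At the next protocol amendment:** change the success sentence in 9.3.5 to the mITT and align the two definitions in 9.2.

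**Cost.** The SAP change is a few lines, with no new data and no effect on sample size. An amendment costs more: protocol 12.3 requires FDA submission and IRB approval before implementation, and 13.5 requires documented approval. SAP 5.1 already describes randomization in the past tense, so conduct may be well advanced. The SAP lines are therefore the proportionate first step.

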9.4 Procedure for Accounting for Missing, Unused, or Spurious Data

For the summarization and analysis of efficacy data, the focus will be on observed case data only. As appropriate, confirmatory efficacy analyses will be performed using imputation for missing data; details of the imputation, if performed, will be included in the study Statistical Analysis Plan. For the summarization of safety data, observed case data only will be used.

9.5 Procedure for Reporting Deviations From the Statistical Plan

Any deviations from the statistical plan will be described and a justification given in the final Clinical Study Report.

10 DIRECT ACCESS TO SOURCE DATA AND DOCUMENTS

The Investigator will permit study-related monitoring visits, audits, IRB review, and regulatory inspection(s) by providing direct access to source data and documents.

11 QUALITY CONTROL AND QUALITY ASSURANCE

The progress of the study will be monitored by onsite, written, and telephone communications between personnel at the Investigator's site and the Medical Monitor. Should the COVID-19 pandemic restrict monitors from traveling to a site, remote review will be conducted to the extent possible, while still ensuring the study is monitored appropriately per applicable regulations and guidelines. The Investigator will allow Ocuphire, the Study Monitor, and the Medical Monitor to inspect all eCRFs, subject records (source documents), signed consent/assent forms, records of study medication receipt, storage, preparation, and disposition, and regulatory files related to this study.

12 ETHICAL CONSIDERATIONS AND GCP COMPLIANCE

12.1 GCP Compliance

The proposed study is subject to all applicable governmental rules and regulations concerning the conduct of clinical trials on human subjects. This includes, but is not necessarily limited to, the approval of IRBs, the Helsinki Declaration, US FDA Law, International Council for Harmonisation (ICH) GCP guidelines, obtaining prospective informed consent, monitoring of the conduct of the study and the completeness of the eCRFs by Ocuphire or its designee(s), and appropriate record retention by the Investigator.

12.2 Institutional Review Board

This protocol, materials used to recruit subjects, and materials used to document consent/assent must be approved by the IRB prior to initiation of the study. Written IRB approval must adequately identify the protocol and informed consent/assent. In addition to approving the protocol, the IRB must also approve the Subject Information and Consent/Assent/Parental Consent Form, as well as any advertising tools that will be used for the study. Copies of all approved materials, all correspondence with the IRB and written approval from the IRB must be made available to Ocuphire, *prior* to the start of subject enrollment into the study.

12.3 Protocol Deviations/Violations

The Investigator should not deviate from the requirements of this protocol without prior written approval of the Medical Monitor or Sponsor except in the event of a medical emergency.

A reportable protocol deviation is defined as nonadherence to the protocol that involves inclusion/exclusion criteria, affects subject safety, rights or welfare, or has the potential to affect the integrity of the data. Examples of major protocol deviations include study enrollment by ineligible subject, loss of key data such as equipment malfunction (e.g., pupillometer), and/or use of a prohibited medication during the study.

All protocol deviations will be reported by entering the event in the appropriate eCRF page. Protocol deviations should be reported to the IRB in accordance with IRB-specific guidelines. If there is any question as to whether the deviation is reportable, Ocuphire or designee and the IRB should be contacted.

All changes to the protocol will be made by the Sponsor or designee as an approved amendment to the protocol, submitted to the FDA, and approved by the IRB prior to implementation.

Changes implemented without prior approval will be considered protocol violations.

12.4 Informed Consent and Assent Requirements

Written informed consent will be obtained from each adult subject. A copy of the signed and dated consent/assent document will be given to each subject or parent guardian. The

original signed and dated informed consent/assent document must be maintained in the study files at the Investigator's site.

The Investigator is responsible for ensuring that no subject is subject to any study-related examination or activity before that subject has given informed consent/assent. The subject must give written consent/assent after the receipt of detailed information. The verbal explanation will cover all the elements specified in the written information provided for the subject.

It should be emphasized that the subject is at liberty to withdraw consent/assent to participate at any time, without penalty or loss of benefits to which the subject is otherwise entitled. Subjects who refuse to give, or withdraw, written informed consent/assent may not be included or continued in this study, but this will not impact their subsequent care.

The Investigator will inform the subject of the aims, methods, anticipated benefits, and potential hazards of the study, including any discomfort it may entail. The subject must be given every opportunity to clarify any points he/she does not understand and, if necessary, ask for more information. At the end of the interview, the subject may be given time to reflect if this is required, or if the subject requests more time. Subjects and/or legal guardian will be required to sign and date the informed consent form.

A copy of the signed and dated consent/assent document will be given to each subject. The original signed and dated informed consent/assent document must be maintained in the study files at the Investigator's site. Signed informed consent/assent must be obtained prior to the conductance of any study procedures.

